#### Assessment of Intensity

The investigator will make an assessment of intensity for each AE and SAE reported during the study and assign it to 1 of the categories listed below (as defined by the NCI CTCAE v5.0 system).

GRADE	Clinical Description of Intensity
1	MILD AE
2	MODERATE AE
3	SEVERE AE
4	LIFE-THREATENING; urgent intervention indicated
5	DEATH RELATED TO AE

#### Assessment of Causality

- The investigator is obligated to assess the relationship between study intervention and each occurrence of each AE or SAE. The investigator will use clinical judgment to determine the relationship.
- A "reasonable possibility" of a relationship conveys that there are facts, evidence, and/or arguments to suggest a causal relationship, rather than a relationship cannot be ruled out.
- Alternative causes, such as underlying disease(s), concomitant therapy, and other risk factors, as well as the temporal relationship of the event to study intervention administration, will be considered and investigated.

- The investigator will also consult the IB and/or product information, for marketed products, in their assessment.
- For each AE or SAE, the investigator **must** document in the medical notes that they have reviewed the AE or SAE and have provided an assessment of causality.
- There may be situations in which an SAE has occurred and the investigator has minimal information to include in the initial report to the sponsor. However, it is very important that the investigator always make an assessment of causality for every event before the initial transmission of the SAE data to the sponsor.
- The investigator may change his/her opinion of causality in light of follow-up information and send an SAE follow-up report with the updated causality assessment.
- The causality assessment is one of the criteria used when determining regulatory reporting requirements.
- If the investigator does not know whether or not the study intervention caused the event, then the event will be handled as “related to study intervention” for reporting purposes, as defined by the sponsor. In addition, if the investigator determines that an SAE is associated with study procedures, the investigator must record this causal relationship in the source documents and CRF, and report such an assessment in the dedicated section of the CT SAE Report Form and in accordance with the SAE reporting requirements.

#### Follow-Up of AEs and SAEs

- The investigator is obligated to perform or arrange for the conduct of supplemental measurements and/or evaluations, as medically indicated or as requested by the sponsor, to elucidate the nature and/or causality of the AE or SAE as fully as possible. This may include additional laboratory tests or investigations, histopathological examinations, or consultation with other healthcare providers.
- New or updated information will be recorded in the originally submitted documents.
- The investigator will submit any updated SAE data to the sponsor within 24 hours of receipt of the information.

#### 10.3.4. Reporting of SAEs

##### SAE Reporting to Pfizer Safety via an Electronic DCT

- The primary mechanism for reporting an SAE to Pfizer Safety will be the electronic DCT.
- If the electronic system is unavailable, then the site will use the paper SAE DCT (see next section) to report the event within 24 hours.
- The site will enter the SAE data into the electronic DCT (eg, eSAE or PSSA) or paper form (as applicable) as soon as the data become available.
- After the study is completed at a given site, the electronic DCT will be taken off-line to prevent the entry of new data or changes to existing data.
- If a site receives a report of a new SAE from a study participant or receives updated data on a previously reported SAE after the electronic DCT has been taken off-line, then the site can report this information on a paper SAE form (see next section) or to Pfizer Safety by telephone.

##### SAE Reporting to Pfizer Safety via the CT SAE Report Form

- Facsimile transmission of the CT SAE Report Form is the preferred method to transmit this information to Pfizer Safety.
- In circumstances when the facsimile is not working, an alternative method should be used, eg, secured (Transport Layer Security) or password-protected email. If none of these methods can be used, notification by telephone is acceptable with a copy of the CT SAE Report Form sent by overnight mail or courier service.
- Initial notification via telephone does not replace the need for the investigator to complete and sign the CT SAE Report Form pages within the designated reporting time frames.

## 10.4. Appendix 4: Contraceptive and Barrier Guidance

For contraception guidelines for tafasitamab and lenalidomide, refer to the local prescribing information. In addition, any PPP or other applicable program required per local regulations for lenalidomide must be followed; details of the PPP for lenalidomide are included in Section 10.4.2.

### 10.4.1. Male Participant Reproductive Inclusion Criteria

Male participants are eligible to participate if they agree to the following requirements during the intervention period and for at least 4 weeks after the last dose of lenalidomide, which corresponds to the time needed to eliminate reproductive safety risk of the study intervention(s):

- Refrain from donating sperm.

PLUS either:

- Be abstinent from heterosexual or homosexual intercourse as their preferred and usual lifestyle (abstinent on a long-term and persistent basis) and agree to remain abstinent.

OR

- Must agree to use a male condom when engaging in any activity that allows for passage of ejaculate to another person even after vasectomy.
- The male participants should be advised of the benefit for a WOCBP partner using a highly effective method of contraception with a failure rate of <1% per year, as described in Section 10.4.4.

In the event that a male participant has discontinued two of the 3 combination therapies and remains on monotherapy: requirements are to be continued for at least 4 weeks after the last dose of lenalidomide monotherapy. No contraception or barrier measures are required for male participants on PF-07901801 or tafasitamab.

### 10.4.2. Female Participant Reproductive Inclusion Criteria

The criteria below are part of Inclusion Criterion No. 1 (Age and Sex; [Section 5.1](#)) and specify the reproductive requirements for including female participants. Refer to [Section 10.4.4](#) for a complete list of contraceptive methods permitted in the study.

A female participant is eligible to participate if she (a) is not pregnant or breastfeeding; and (b) agrees not to donate eggs (ova, oocytes) for the purpose of reproduction from the time of screening through 90 days after the last dose of study intervention; and (c) at least 1 of the following conditions applies:

- Is not a WOCBP (see definition in [Section 10.4.3](#)).

OR

- Is a WOCBP and agrees to use a contraceptive method that is highly effective (failure rate of <1% per year) with low user dependency during the intervention period and agrees to use it for at least 90 days after the last dose of study intervention, which corresponds to the time needed to eliminate any reproductive safety risk of the study intervention(s). The investigator should evaluate the effectiveness of the contraceptive method in relationship to the first dose of study intervention.

OR

- Is a WOCBP and agrees to use a highly effective (failure rate of <1% per year) user-dependent method of contraception during the intervention period and for at least 90 days after the last dose of study intervention, which corresponds to the time needed to eliminate any reproductive safety risk of the study intervention(s). In addition to her use of the highly effective method above, she agrees to concurrently use an effective barrier method. The investigator should evaluate the effectiveness of the contraceptive method in relationship to the first dose of study intervention.

In the event that a WOCBP participant has discontinued 2 of the 3 combination therapies and remains on monotherapy: the contraceptive method must be used for at least 45 days after the last dose of PF-07901801 monotherapy, for at least 28 days after the last dose of lenalidomide monotherapy and/or for at least 90 days after the last dose of tafasitamab.

The investigator is responsible for review of medical history, menstrual history, and recent sexual activity to decrease the risk for inclusion of a woman with an early undetected pregnancy. This is to be documented in the source documentation.

#### **10.4.3. Woman of Childbearing and Non-Childbearing Potential**

A woman is considered fertile following menarche and until becoming postmenopausal unless permanently sterile (see below).

If fertility is unclear (eg, amenorrhea in adolescents or athletes) and a menstrual cycle cannot be confirmed before the first dose of study intervention, additional evaluation should be considered.

Women in the following categories are not considered WOCBP:

1. Premenopausal female with 1 of the following:

- Documented hysterectomy;
- Documented bilateral salpingectomy;
- Documented bilateral oophorectomy.

For individuals with permanent infertility due to a medical cause other than the above (eg, mullerian agenesis, androgen insensitivity), investigator discretion should be applied to determining study entry.

Note: Documentation for any of the above categories can come from the site personnel's review of the participant's medical records, medical examination, or medical history interview. The method of documentation should be recorded in the participant's medical record for the study.

2. Postmenopausal female:

- A postmenopausal state is defined as no menses for 12 months without an alternative medical cause. In addition,
  - A high FSH level in the postmenopausal range must be used to confirm a postmenopausal state in women under 60 years of age and not using hormonal contraception or HRT.
  - A female on HRT and whose menopausal status is in doubt will be required to use one of the highly effective non-estrogen hormonal contraception methods if she wishes to continue her HRT during the study. Otherwise, she must discontinue HRT to allow confirmation of postmenopausal status before study enrollment.

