**Table 1. Study Schedule of Assessment**

Visit Identifier	Screen	On-Treatment Period (28-day Cycle)												Notes			
		Cycle 1				Cycle 2-3				≥Cycle 4				EOT	FU visits		LTFU
Cycle Day	≤28d	D1	D4	D8	D15	D22	D1	D8	D15	D22	D1	D15	7d	28d	90d	Q12W	
 
Day relative to start of study intervention (Day 1).
 

Visit Window		(±1d)	(±2d)	(±2d)	(±2d)	(±2d)	(±2d)	(±2d)	(±2d)	(±2d)	(±2d)	(±2d)	(±2d post-last TX)	(28-35d post-last TX)	(+7 post-last TX)	(±14d post 90d FU)	
 
After 1 year of study intervention, cycle visit date windows are ±7d.
 

HIV status	X																
 
For participants with known history of HIV: CD4 count and viral load
 

Hepatitis B/C panel	X																
 
Monitor participants for HBV reactivation throughout the study, if applicable.
 
See Appendix 2, Appendix 10, and REVIMID SmPC.
 

Pregnancy test (WOCBP only)	X	X		X	X	X	X	X*		X	X*		X				
 
Pregnancy test will be done weekly at C1; and monthly at C2 and beyond.
 
*: WOCBP participants with irregular cycles should have the test done every 2 weeks.
 
See Section 8.3.5 for additional information.
 

Contraception check	X	X					X			X			X	X			
 
Only required for WOCBP and men with WOCBP partner.
 
See Section 4.2.3 and Appendix 4 for additional information.
 

FSH	X																
 
For confirmation of postmenopausal status.
 

Hematology	X	X	X	X	X	X	X	X	X	X	X	X	X				
 
May be collected up to 72 hours prior to dosing visit date.
 
See Appendix 2.
 

PFIZER CONFIDENTIAL

CT02-GSOP Oncology Clinical Protocol Template (01 April 2022)

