**Steps the Healthcare Professional must follow for this protocol:**

[figure not shown]
1. Receive Healthcare Professional/Prescriber PPP educational materials (as supplied by the Sponsor and specific by region);
2. Inform the participant regarding the benefits and risks of treatment with lenalidomide, not sharing lenalidomide, not donating blood, risks associated with fetal exposure, and the necessity to take adequate measures to avoid fetal exposure to lenalidomide;
3. Give the participant the appropriate corresponding educational brochure (for participants of childbearing potential, for participants not of childbearing potential, or for male participants) and counsel the participant on contraception requirements and emergency contraception use (in countries where available);
4. Apply steps from the PPP algorithm (see [Figure 4](#)). The Healthcare Professional must evaluate the participant from a reproductive potential point of view prior to the start of the study and every 4 weeks prior to dispensing lenalidomide, to ensure that:
  - Male participants are informed that they must use condoms if engaging in sexual intercourse with pregnant women or women of childbearing potential (even if the participant had a vasectomy) and must not donate sperm during lenalidomide treatment and for **4 weeks after cessation of lenalidomide**.
  - Female participants must meet one of the following conditions to be considered of non-childbearing potential:
    - Aged 50+ and naturally occurring amenorrhea of over 1 year (amenorrhea that occurred as a result of cytostatic therapy or during breastfeeding period does not exclude the possibility that the participant is fertile);
    - Premature ovarian failure that was confirmed by a gynecologist;
    - Bilateral salpingo-oophorectomy or hysterectomy as part of medical history;
    - XY genotype, Turner syndrome, uterine agenesis.
  - Female participants of childbearing potential must be informed of the necessity to:
    - Utilize highly effective contraceptive method(s) as per the PPP or other applicable program for 4 weeks before treatment, during treatment, and for 90 days after complete cessation of treatment [4 weeks after cessation is the standard timing for lenalidomide but note that a longer duration is required per

SmPC for MINJUVI (tafasitamab)], including during temporary discontinuation of treatment; or

- To maintain total and continuous abstinence; and

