### **Definition of Woman of Childbearing and Non-Childbearing Potential**

A woman is considered fertile following menarche and until becoming postmenopausal unless permanently sterile (see below).

If fertility is unclear (eg, amenorrhea in adolescents or athletes) and a menstrual cycle cannot be confirmed before the first dose of study intervention, additional evaluation should be considered.

- Women in the following categories are not considered WOCBP:

1. Premenopausal female with 1 of the following:

- Documented hysterectomy;
- Documented bilateral oophorectomy.

Note: Documentation for any of the above categories can come from the site personnel's review of the participant's medical records, medical examination, or medical history interview. The method of documentation should be recorded in the participant's medical record for the study.

2. Postmenopausal status is defined as no menses for 24 months without an alternative medical cause (eg, anti-tumor therapy). In addition,

- A high FSH level in the postmenopausal range must be used to confirm a postmenopausal state in women under 60 years of age and not using hormonal contraception or HRT.
- A female on HRT and whose menopausal status is in doubt will be required to use one of the non-estrogen hormonal highly effective contraception methods if they wish to continue their HRT during the study. Otherwise, they must discontinue HRT to allow confirmation of postmenopausal status before study enrollment.

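### Appendix 4 of the protocol defines childbearing potential in two ways that disagree in both directions, and no sentence says which definition governs

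*Protocol*

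**What the plan says.** **Section 10.4.3** lists the women who are not WOCBP. The surgical categories are hysterectomy, "Documented bilateral salpingectomy" and bilateral oophorectomy, and any one is enough. The menopausal category reads "A postmenopausal state is defined as no menses for 12 months without an alternative medical cause". It has no age floor, but below 60 it adds a laboratory condition: "A high FSH level in the postmenopausal range must be used to confirm a postmenopausal state in women under 60 years of age", for women not using hormonal contraception or HRT. Other causes of permanent infertility are left to the investigator's discretion.

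**Section 10.4.5**, under the steps the healthcare professional must follow, sets a separate test: "Female participants must meet one of the following conditions to be considered of non-childbearing potential". The conditions are:
- "Aged 50+ and naturally occurring amenorrhea of over 1 year";
- "Premature ovarian failure that was confirmed by a gynecologist";
- bilateral salpingo-oophorectomy or hysterectomy;
- XY genotype, Turner syndrome or uterine agenesis.

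Every woman outside that list must use highly effective contraception or remain totally abstinent. She must also have pregnancy tests every 4 weeks, at end of treatment and 4 weeks after lenalidomide stops.

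**Which rules use which term.** Section 10.4.2 lets a woman meet the contraception condition by not being a WOCBP and cites 10.4.3 for the meaning. Section 8.3.5 tests WOCBP. The Schedule of Activities row is headed "Pregnancy test (WOCBP only", and the contraception-check row is limited to WOCBP and men with a WOCBP partner.

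**The concern.** The protocol's risk assessment expects lenalidomide to be teratogenic in humans, so deciding who is tested and who must use contraception is a safety-critical classification. Appendix 4 makes that classification twice, by different criteria. One version feeds eligibility and the visit schedule; the other feeds the steps around dispensing lenalidomide. A site that starts from 10.4.2 and one that starts from 10.4.5 can place the same woman in opposite groups, and each can cite the protocol.

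The opening of Appendix 4 makes this more likely. It sends the reader to 10.4.2 for the details of the pregnancy prevention program, and 10.4.2 leads on to 10.4.3. The program itself is in 10.4.5.

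**Working it through.** No power, error rate or event count is involved and the plan gives no figure to reproduce. The check sets the two lists side by side and then traces which rules depend on which list.

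**Step 1. Apply both lists to the same women.**

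| Case | Section 10.4.3 | Section 10.4.5 | Agree? |
|---|---|---|---|
| (a) Age 47, 13 months of natural amenorrhea, high FSH, no hormonal contraception or HRT, ovarian failure not confirmed by a gynecologist | Not WOCBP | Childbearing potential | No |
| (b) Premenopausal, bilateral salpingectomy alone | Not WOCBP | Childbearing potential | No |
| (c) Premenopausal before surgery, bilateral oophorectomy alone | Not WOCBP | Childbearing potential | No |
| (d) Age 52, natural amenorrhea over 1 year, no FSH result, no hormonal contraception or HRT | Not confirmed postmenopausal, so still WOCBP | Not of childbearing potential | No |
| (e) Hysterectomy | Not WOCBP | Not of childbearing potential | Yes |

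Cases (a) to (c) split one way and case (d) the other, so neither list is uniformly stricter. The inclusion criteria admit adults from 18 years, so none of these women is ruled out by age.

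**Step 2. Locate the disagreement.** It is not the length of amenorrhea, since 12 months and over 1 year nearly coincide. It lies in three places: the age-50 condition, present only in 10.4.5; the FSH condition, present only in 10.4.3; and the surgical categories, where 10.4.3 accepts removal of tubes alone or ovaries alone and 10.4.5 lists only the combined operation or hysterectomy.

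**Step 3. Follow case (a) through the rules.**
- Eligibility, 10.4.2: she qualifies as not a WOCBP, with no contraception commitment.
- Section 8.3.5 and the schedule rows: the scheduled tests and contraception checks are not assigned to her, because they are for WOCBP.
- Section 10.4.5: she must use contraception or be abstinent, be tested every 4 weeks, and have a negative test before lenalidomide is dispensed.

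**Step 4. Look for a sentence that settles it.**
- Section 10.4.5 opens by making its requirements additional to the protocol's own. That makes the duties cumulative but does not redefine WOCBP elsewhere.
- Section 10.4.4 has a most-stringent rule, but its subject is contraceptive methods, not who is of childbearing potential.
- Section 4.2.3 applies the program unless there is reliable evidence of no childbearing potential, without saying which section sets that standard.

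None of the three states which definition governs.

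**Step 5. Test the additive reading.** Suppose a site treats a woman as of childbearing potential if either section says so. Case (a) then falls under the 4-weekly tests of 10.4.5. It stays unclear whether she also gets the weekly Cycle 1 tests, because the schedule gives those to WOCBP only. The most protective reading therefore still leaves a gap that sites must fill themselves.

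**The case against.** The strongest reply is that the protocol, read whole, already protects these women. Section 10.4.5 is expressly additive. It has reproductive potential evaluated before the study and every 4 weeks before lenalidomide is dispensed, and it requires a negative test before dispensing. Section 8.3.5 requires any further tests in the local lenalidomide label and sends the reader to 10.4.5. Inclusion criterion 1 cites 10.4.5 beside 10.4.2, and Section 4.2.3 and the risk table also invoke the program.

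This stands, and it rules out a stronger reading that a reader might infer: that a woman who is not a WOCBP under 10.4.3 is exempt from tests and contraception while on lenalidomide. It also means that counting the tests in the schedule against none does not measure what would be missed, since 10.4.5 has its own testing schedule and label-driven tests come on top.

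A reader might also take the Japan definition ("Postmenopausal status is defined as no menses for 24 months without an alternative medical cause") as a third conflicting rule. It is not: Section 10.10.2 presents it as a country-specific requirement for Japanese participants, added to Appendix 4.

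Two further points have weight. The sections differ in scope, since 10.4.5 concerns lenalidomide while 10.4.2 and 10.4.3 cover all three drugs, including the period after lenalidomide ends. Two definitions could therefore be deliberate, but the protocol does not say so. Site practice also depends on regional program materials that are not in the documents.

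What the reply does not supply is a sentence saying which definition applies when.

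**Conclusion.** The contradiction is real and can be checked from the text. Appendix 4 classes the same woman differently in at least four situations, in both directions, and leaves the choice to the site. It is a conflict in a safety-critical classification, not an exemption: on the whole-protocol reading, 10.4.5 still applies while lenalidomide is given.

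The size cannot be expressed as a number. The documents do not say how many women fall in the disputed categories. The count cannot exceed the number of women among the approximately 20 participants planned for Phase 1b, and Phase 2 will not be initiated. The point still matters for anyone on treatment, since Section 10.1.10 allows participants to continue until the end of the study after a termination unrelated to safety. No efficacy or safety analysis depends on it.

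The conclusion assumes only that each list is applied as written. It takes no position on which definition is clinically right.

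**What to change.** - Reconcile 10.4.3 and 10.4.5 into one definition, or keep both and state which governs for which drug and period. The choice belongs to the sponsor's clinical and safety functions.
- Make 10.4.2, Section 8.3.5 and the schedule rows for pregnancy tests and contraception checks cite the resulting definition.
- State which test schedule applies to a woman captured by only one of the two sections, if both are kept.
- Correct the pointer at the start of Appendix 4 so that it leads to 10.4.5 for the pregnancy prevention program.

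The cost is protocol wording and notice to sites. Some women may be reclassified, in a direction that depends on the definition chosen. Sample size, data collection for the endpoints and the SAP are unaffected.
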